Per ISO 14155: 2011-Clinical investigations shall be conducted in accordance with the ethical principles that have their origin in the Declaration of Helsinki. These principles protect the rights, safety and well-being of human subjects, which are the most important considerations and shall prevail over interests of science and society. These principles shall be understood, observed, and applied at every step in the clinical investigation. All parties involved in the conduct of the clinical investigation shall share the responsibility for its conduct in accordance with their respective roles in the clinical investigation. Each site must be identified in the main Research Ethics application and have written approval from their

Trust R&D department prior to enrolling subjects. Any subsequent study amendment must also be submitted to the MREC for opinion and have individual Trust approval prior to implementation. This study will be registered with ClinicalTrials.gov.

Financial Disclosures

All Investigators must complete, sign and date the Financial Disclosure form prior to their participation in the clinical study. Each Investigator must notify Wright Medical or its designated representative if any relevant changes occur during the course of the study and for one year following the completion of the study. Copies of the Financial Disclosure form for each Investigator will be maintained in the sponsor's investigational files.

Sponsor Discontinuation Criteria

Wright Medical reserves the right to terminate a non-performing site. Reasons for considering early termination or suspension of an individual site may include, but are not limited to:

- Site non-compliance with study protocol or failure to comply with government or local regulations
- Failure to submit data in a timely manner
- Failure to comply with or act upon findings
- Failure to maintain pace to complete enrollment

Wright Medical reserves the right to discontinue the study at any time and will notify each investigator immediately at the time of such a decision. Formal documentation will be provided to the investigators to notify their IRB/EC/REC, research institutions. After such a decision, the Investigator must contact all participating subjects to notify them of this decision and its impact on their follow-up.

STUDY COMPLETION

Subject Completion

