Inclusion Criteria	
Subjects to be included in the study must meet all of the following criteria:
 
 • Be 21 years of age at the time of surgery; • Diagnosed with unilateral and/or bilateral ankle joint disease; • Diagnosed with ankle joint damage from rheumatoid arthritis, post-traumatic, or degenerative arthritis; • Willing and able to consent to participate (written, informed consent / witnessed verbal consent) • Willing and able to attend the requested follow-up visits; • Subjects determined by the Investigator to be an appropriate candidate for the INFINITY® Total Ankle System
Exclusion Criteria	
Subjects will be excluded from the study if they meet any of the following criteria:
 
 • Subjects with an ankle condition, as determined by the investigator, to be an inappropriate candidate for a total ankle replacement; • Subjects requiring revision total ankle replacement of the ankle being considered for study

SCHEDULE of EVENTS

Procedures	Pre-op	Op.	6 mo +/-30 days	1 yr +/-60 days	2 yr +/-60 days	5 yr +/-60 days	7 yr +/-60 days	10 yr +/-60 days	Study Close
Informed Consent	X								
Inclusion/Exclusion Criteria	X								
Medical History/Demographics	X								
Operative (Surgical) procedure/device		X							
EQ5D5L	X		X	X	X	X	X	X	
Ankle Osteoarthritis Score (AOS)	X		X	X	X	X	X	X	
Manchester-Oxford Foot Questionnaire	X		X	X	X	X	X	X	
Radiographic Assessment (Investigator requirement) ¹	X		X	X	X	X	X	X	
Adverse Event Assessment		X	X	X	X	X	X	X	
End of Study									X
Surgical Intervention ²									
*Sponsor-approved Unscheduled Visit ³									

¹Standard Clinical Care Radiographic assessment (X-Rays) will be collected annually as part of standard clinical care. No research specific X-rays will be taken during the study.

²&³ These are not scheduled time point events but will be observed for throughout study participation.

INTRODUCTION

Wright Medical introduced the INFINITY®, a CE Marked total ankle system, for use in total ankle arthroplasty replacement (TAR) in the United States, Canada, and Europe, including the UK in 2014. The INFINITY® Total Ankle System is a fixed-bearing, bone-sparing total ankle prosthesis that restores mobility to a failing ankle joint. It encompasses three components (i.e., tibial tray, tibial insert, and talar dome).

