There are no additional risks anticipated, specific to participating in this study. The study is not examining any experimental procedures and participation in the study is not predicted to affect the medical treatment received by enrolled subjects. The INFINITY® Total Ankle does not pose additional risks compared to other standard total ankle systems when used for the same clinical application. The risks of ankle replacement include intra-operative complications such as peri-prosthetic fracture, neurovascular damage and tendon injury. Early post-operative problems include infection, wound healing problems, deep vein thrombosis, and peri-prosthetic fracture. Late complications include infection, peri-prosthetic fracture, loosening, implant failure, ongoing pain. These risks are comparable to those in alternative implants and alternative surgical procedures.

STUDY DESIGN

Study Design

The selected design is a multi-center, non-randomized, prospective study of 500 subjects in the UK with ten investigational sites and a potential for more as needed to meet the enrollment requirements. The study subjects included are those with ankle joints damaged by severe rheumatoid arthritis, post-traumatic disease, and degenerative arthritis and implanted with the INFINITY® Total Ankle System.

Primary and Secondary Endpoints

The primary endpoint is a survivorship rate at 10 years as defined with a Kaplan Meier survivorship analysis. Secondary endpoints identify, assess and compare functional improvements or deviations collected through investigator observation and patient self-reporting, and include:

- Identification and assessment of the implant through radiographic assessment for component loosening and/or subsidence, any osteolysis and/or cyst formation early and throughout the lifetime of the implant.

- Comparison of improvements in self-reported pain and social interaction for quality of life measures from pre-op through 10 years post operatively; assessed by EQ5D5L.
- Comparison of pain and functional improvement from pre-op through 10 years in the AOS which is a visual analogue scale specifically designed as a modification of the Foot function Index.
- Comparison of the improvements in self-reported function scores from pre-op through 10 years post-operatively, assessed by MOXFQ walking/standing scores.
- Identification and reporting on the safety of the implant in terms of complications and adverse events.

[figure not shown]

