Planned visits and Follow-Up Time Points

Subjects will be seen prospectively at the following intervals Pre-Op, Operative, 6 months, 1, 2, 5, 7, and 10 years. If there are special circumstances where the subjects require a visit outside the windows of the established visits, the investigator may seek approval from Wright Medical for an acceptance of an “unscheduled visit” and it will be determined if the data will be included and analyzed.

SITE/SUBJECT SELECTION

Clinical Research Sites will be identified to participate in the study based on current experience, and training in the use of the INFINITY® Total Ankle System and according to ICH GCP guidelines and ISO 14155: 2011 which states; qualified by education, training and experience to perform his or her respective task(s). It is the expectation the surgeon will adhere to and follow the INFINITY® Surgical Technique and have knowledge of the contraindications as provided in the Instructions for Use (IFU). (See Appendix A).

Study Design Summary

Informed Consent

Subjects will be recruited based on interest in participating in the study. All subjects will be consented by an appropriately trained clinician or research nurse using the REC approved information sheet and consent form in order to participate in the study and prior to any data collection, or any study procedure. The study clinician or research nurse will assess whether the patient can give informed consent or not during the consent process, in compliance with the 2005 Mental Capacity Act. The potential participant must be allowed ample time to review the informed consent and should be allowed to take the time to read, review, ask questions, and receive answers as well as being fully informed of all aspects of the study before a decision is made to participate. The source documentation will include a statement of the consent process and include details of the person taking consent for study participation.

Screening

Subjects with interest in participating in the study, after signing the informed consent document, will then be invited to participate if they meet the Inclusion Criteria.

Point of Enrollment

Subjects will be considered enrolled in the study when they have:

- Been informed of all aspects of the study and have signed or have their verbal consent witnessed on the Informed Consent document
- Acknowledged the appropriate patient data release information (included in the Informed Consent document)

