- Satisfied the Inclusion/Exclusion Criteria
- Implanted with the Device

Investigators should document subject enrollment by completing the screening and enrollment logs located within the trial master file. The Source documentation should clearly state that all inclusion and exclusion criteria have been met and the patient data release and informed consent documents have been signed and appropriately dated prior to any study related activity,

The investigative sites will be assigned three digit a site code ***, and at enrollment the subject will be assigned a sequential subject identification number corresponding to the order the subject was enrolled (i.e. the first subject enrolled at each site will be site number *** followed by subject identifier 001). The assigned codes will be used to identify the subject on all case report forms. All investigative sites will be provided protocol training of the during the site initiation visits. Investigative sites will be provided paper case report forms/booklets, which may be used as source documentation, these must signed by the individual completing the form; i.e., coordinator, patient, or investigator.

Study Duration, Subject Participation and Estimated Enrollment Period

The total study duration from , first patient, first visit, (FPFV) to last patient, last visit (LPLV) is expected to be 13 years, with a recruitment period of 36 months The investigator/investigative site must make every reasonable attempt to contact the patients to complete all scheduled post-operative visits within the visit window. In instances where the individual cannot be reached, the investigator/investigative site will document at least two attempts to contact the

patient via phone/mail and one certified letter for each time point. Due to the length of this study and the risk of lost to follow-up potential, if a subject has an inability to and, for some unforeseen reason cannot be seen on the hospital site, patient reported outcome measure case report forms may be completed remotely by post or telephone and returned to the investigative site/investigator for review and submission. If this process is applied it must be documented and reported to Wright accordingly.

Subject Withdrawal or Discontinuation

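### Recruitment rests on interest in the study, with no consecutive offer and an undefined screening log, so the protocol does not ensure that the capture rate behind the 10-year survivorship figure is known

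*Protocol*

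**What the plan says.** The protocol section SITE/SUBJECT SELECTION describes recruitment in one sentence, under Informed Consent: "Subjects will be recruited based on interest in participating in the study". Under Screening, interested subjects, "after signing the informed consent document, will then be invited to participate if they meet the Inclusion Criteria".

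Two inclusion criteria bear on who enters: "Willing and able to attend the requested follow-up visits" and "Subjects determined by the Investigator to be an appropriate candidate for the INFINITY® Total Ankle System". Under Point of Enrollment, a subject counts as enrolled after consent, data release and eligibility are complete and the subject has been "Implanted with the Device".

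On records, the same section says: "Investigators should document subject enrollment by completing the screening and enrollment logs located within the trial master file". It does not say whether the screening log lists patients who were not approached or who declined.

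Primary and Secondary Endpoints gives the target: "The primary endpoint is a survivorship rate at 10 years as defined with a Kaplan Meier survivorship analysis". Study Design describes a non-randomised study of 500 subjects with one device and no comparator. The Introduction says the data should show how the product is used and performs in the UK.

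**The concern.** A single-arm survivorship rate has no internal comparison, so its meaning depends on which patients are in the series. If each site decides whom to approach, patients expected to do better or worse can be over-represented. The only protection is a rule on whom to approach, or a count of those missed that lets a reader judge the scope for selection. The protocol provides no such rule and does not ensure the count.

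The Study Rationale sends the results to regulatory authorities and notified bodies, and Sample Size links the study to the precedent of national implant ratings. Those readers will want to know whether the rate describes the device in UK hands or a subset of unknown share. Recruitment is limited to 36 months, and a denominator not recorded in that time is hard to reconstruct later.

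**Working it through.** **Reading the text.** Four places could supply the missing rule or count.

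1. *Informed Consent and Screening*: interest, then consent, then eligibility. There is no instruction on whom to approach.
2. *Point of Enrollment*: logs are required, with the stated purpose of documenting enrolment. Their content is undefined. Because eligibility is assessed after consent, the screening log may begin only with consented patients, but the text does not settle this. Subject numbers run in order of enrolment within each site, so they leave no trace of missed patients.
3. *Monitoring Plan*: site staff must understand subject selection procedures, but none is given for approaching patients. The listed monitoring checks do not compare enrolments with implantations.
4. *Sample Size*: 500 is expressly not a statistical calculation. No expected survivorship or capture rate is given, so there is no protocol figure to reproduce.

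**Illustration of size.** Let c be the share of INFINITY recipients enrolled, F the 10-year failure risk in those enrolled, and RR the failure risk of non-enrolled relative to enrolled recipients. Then:

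- failure in all recipients = F × [c + (1 − c) × RR]
- overstatement of survivorship = F × (1 − c) × (RR − 1)

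F = 10%, c and RR are assumptions; only n = 500 comes from the protocol.

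- c = 0.8, RR = 1.25: 10 × 0.2 × 0.25 = 0.5 points
- c = 0.7, RR = 1.5: 10 × 0.3 × 0.5 = 1.5 points
- c = 0.5, RR = 2: 10 × 0.5 × 1 = 5 points

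Overstatement in percentage points over a wider range:

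| Capture | RR 1.25 | RR 1.5 | RR 2.0 |
|---|---|---|---|
| 90% | 0.25 | 0.5 | 1.0 |
| 80% | 0.5 | 1.0 | 2.0 |
| 60% | 1.0 | 2.0 | 4.0 |
| 50% | 1.25 | 2.5 | 5.0 |
| 40% | 1.5 | 3.0 | 6.0 |

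**Yardstick.** The 95% half-width at 90% survivorship, n = 500 and no censoring is 1.96 × √(0.90 × 0.10 / 500) = 1.96 × 0.01342 = 0.0263, or about 2.6 points. Bias exceeds this when (1 − c)(RR − 1) > 0.263:

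- RR 2: capture below about 74% (1 − 0.263)
- RR 1.5: capture below about 47% (1 − 0.263/0.5)
- RR 1.25: at no capture rate, since 0.263/0.25 is above 1

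An RR below 1 reverses the sign.

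**Workload.** 500/36 = 13.9 enrolments per month, or 1.2 per site with the synopsis's 12 sites and 1.4 with Study Design's ten. Implant volume is not given, so the number of recipients to be counted is unknown.

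**The case against.** The strongest reply is that this is an omission, not an error. Every consented cohort consists of willing patients, and the sentence on interest, placed under Informed Consent, may only express voluntariness. Consent and eligibility come before surgery, so enrolment cannot be selected on observed implant outcome. Diagnosis, BMI, smoking, comorbidity, previous surgery and deformity grade are collected, so case mix can be described and results standardised on measured factors. At high capture the bias is small against sampling error.

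Most of this stands and limits the point. Any selection acts through prognosis as seen before surgery, and part of it can be examined. But describing enrolled patients does not show who was left out, and standardising needs a target population that the protocol does not require anyone to record. The reply that bias is small at high capture also depends on knowing the capture rate.

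Three stronger readings are tempting but not supported:

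- *That the capture rate cannot be known, or that the log omits patients not approached or declining.* The log is required and its content is unstated; a site could record them.
- *That screening after consent is itself a defect.* The protocol requires consent before data are collected or study procedures begin, so the order follows from that rule. It matters only because it may shorten the log.
- *That the investigator's suitability criterion lets surgeons leave out unfavourable recipients.* The criterion concerns suitability for the device. A patient judged unsuitable would not be expected to receive it, and so falls outside the population of recipients.

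**Conclusion.** The point holds in limited form. The protocol sets interest as its recruitment rule, requires no consecutive offer, and leaves the screening log undefined. It therefore does not ensure that the capture rate will be known. Selection on pre-operative prognosis could bias the single survivorship rate, and analysis of the enrolled data alone could not fully bound that bias.

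Neither size nor direction can be taken from the documents. Under the assumptions shown, the effect runs from negligible (0.5 points at 80% capture and relative risk 1.25) to about twice the sampling half-width (5 against 2.6 points at 50% capture and relative risk 2). A reader might infer that reported survivorship will be too high; that rests on assuming that missed patients fare worse, which the documents do not say. Only the protocol was reviewed, but whom to approach is a protocol matter, and an SAP would not normally settle it.

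**What to change.** Three changes:

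- **Informed Consent:** replace the interest sentence with a rule that every consecutive patient listed for an INFINITY replacement at a participating site during recruitment is offered the study, with participation remaining voluntary.
- **Point of Enrollment:** define the screening log as holding non-identifying aggregate counts per site of patients implanted with the device, approached, declined (with the reason if offered), ineligible and enrolled.
- **Reporting:** give the capture rate by site (enrolled divided by implanted) beside the survivorship estimate.

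The counts should stay aggregate. Patient-level entries such as age band or deformity grade for people who have not consented would have to be reconciled with the protocol's rule of consent before data collection, and could identify individuals at low monthly volumes.

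The cost is a small logging burden at each site and a protocol amendment, which under Amendments to Study Protocol and Statements of Compliance needs ethics committee and individual Trust approval. Sample size, visits and treatment do not change.

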Subjects maintain the right to discontinue their participation in the study at any point without penalty or loss of benefit to which the subject is otherwise entitled per ICH E6 4.8.10(m) guidelines. Although, a subject is not obliged to give his or her reason(s) for withdrawing prematurely from this study, the investigator should make a reasonable effort to ascertain the reason(s), while fully respecting the subject's rights per ICH E6 4.3.4 guidelines.

Device Failure

Subjects will be considered a treatment failure, and will be withdrawn from the study if any sections of the device (tibial or talar metal components) have been removed at any time during their participation. This should be reported onto the adverse event form. In addition, any surgical intervention during study participation that relates to their total ankle replacement will be reported on the surgical intervention case report form.

Procedures and Case Report Forms

Subject medical history and demographic information will be collected and recorded onto the demographic case report form. The following information will be collected on these forms:

- Date of birth
- Gender
- Height
- Weight
- BMI calculation
- Smoking status
- Status of other joints that affect ambulation (i.e., knee replacement, contralateral arthritis and/or ankle replacement)
- Concomitant health conditions (diabetes and other medical conditions, etc.)

Operative Procedure Information

The information related to the subject's operation will be collected and recorded according to the Operative Information Case Report Forms. The following operative information related to the primary TAR procedure will be documented on these forms:

- Primary diagnosis
- Any previous surgery to index joint
- Date of operation
- Site location
- Surgical approach
 - Instrumentation type (standard) or (additional approved INFINITY® instrumentation)

- List concomitant operative procedures such as tendon/deltoid lengthening or other reconstructive process required to make final implantation correct
- Cement use
- Intraoperative complications (to be collected on the Adverse Event Case Report Form)
- Product description and eight-digit product code for all components implanted

Patient Reported Outcome Measures (PROMS)

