relevant to the safety and survivorship of the implant but, also to provide assurances that for the introduction of new implants, a data collection plan is in place for ongoing evaluations and reporting.

The information gained from this data collection will be analyzed at times based on potential publication periods around 3, 5, and 7 years with a final analysis after all subjects have completed all follow-up requirements at the 10 year final visit. In addition, at time points determined by the investigators and/or Wright Medical will be evaluated as needed or required for additional analysis of data for reporting and/or publication purposes will be done throughout the study.

Demographics

Descriptive statistics will be applied for the demographic data of all subjects. Pre to post-operative comparisons will be made for all outcome measures at the specific data collection time points. Summary statistics for continuous variables may include subject count, mean, standard deviation, minimum and maximum values.

ADVERSE EVENTS

Suspected Unexpected Serious Adverse Reactions (SUSARS), Serious Adverse Events (SAE's) & ADVERSE EVENTS (AE's)

Procedural and device related events will be described and collected on the AE form. It is the responsibility of the operating surgeon/s to be aware and note the adverse effects from the package insert/instructions for use by the manufacturer/sponsor. (See appendix A) The number of subjects experiencing each adverse event percentage or proportion of the total number of subjects experiencing each adverse event will also be reported. All adverse events shall be reported in an interim and/or final report of the clinical investigation. All device deficiencies related to the identity, quality, durability, reliability, safety or performance of the investigational medical device shall be documented throughout the clinical investigation and appropriately managed by the sponsor.

Potential intraoperative and early postoperative complications, related to all total ankle replacements may include:

- pain;
- sudden drop in blood pressure intra-operatively due to the use of bone cement;
- damage to blood vessels;
- temporary or permanent nerve damage resulting in pain or numbness of the affected limb;
- cardiovascular disorders including venous thrombosis, pulmonary embolism, or myocardial infarction.
- hematoma;
- delayed wound healing; and
- deep wound infection (early or late) which may necessitate removal of the prosthesis.

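### Enrolment and the subject number wait for implantation, so an operation started but ended without the device has no assured place in the procedural complication rate

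*Protocol*

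**What the plan says.** Under Point of Enrollment, the list of conditions opens with "Subjects will be considered enrolled in the study when they have" and names consent, acknowledgement of the data release information, fulfilment of the eligibility criteria and, last, "Implanted with the Device". The same section states that "at enrollment the subject will be assigned a sequential subject identification number corresponding to the order the subject was enrolled", and then: "The assigned codes will be used to identify the subject on all case report forms". Participant Confidentiality adds that the electronic case report form identifies participants by study number alone.

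On safety, Primary and Secondary Endpoints includes "Identification and reporting on the safety of the implant in terms of complications and adverse events". Operative Procedure Information lists "Intraoperative complications (to be collected on the Adverse Event Case Report Form"), the Adverse Events section says "Procedural and device related events will be described and collected on the AE form", and the Schedule of Events starts adverse event assessment at the operative visit. The Adverse Events section expresses each event as a proportion of the total number of subjects. Under Risks, the protocol says: "The risks of ankle replacement include intra-operative complications such as peri-prosthetic fracture, neurovascular damage and tendon injury".

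The Synopsis and Study Design describe the study group as patients implanted with the device. For a patient who consents but is not implanted, the only record that Point of Enrollment names is the screening and enrolment log. The protocol has no rule for an operation that is started and ends without the device.

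**The concern.** Entry to the group whose procedural complications are counted depends on the procedure having been completed. That suits survivorship, because an implant that was never placed cannot survive or fail. It does not suit intra-operative events, which arise whether or not the device is finally placed and can be the reason it is not.

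A case abandoned because of a complication would then be missing from both the numerator and the denominator of the procedural complication rate. Study Rationale says that results go to regulatory authorities and notified bodies, and the Introduction says that little has been published on this device. The denominator behind its complication rates should therefore be plain.

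**Working it through.** The protocol states no figure on this point, and its sample size of 500 was not calculated statistically, so there is nothing to reproduce. The check is a reading of the text, followed by an illustration of size.

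**Reading the text**

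1. Enrolment needs all the listed conditions, including implantation (Point of Enrollment).
2. The number is given at enrolment, hence not before implantation (same section).
3. That number identifies the subject on every case report form (same section) and is the only identifier on the electronic form (Participant Confidentiality).
4. Intra-operative complications are recorded on the Adverse Event form (Operative Procedure Information), and procedural events are within the collected events (Adverse Events).
5. Proportions are taken over the total number of subjects (Adverse Events), and the study group is implanted patients (Synopsis, Study Design).

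Under steps 1 to 3, a started but abandoned case has no number under which an Adverse Event form would be entered. Under step 5, it is not in the described denominator. No other section brings it back.

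**Size, by assumption**

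Inputs: 500 implanted subjects (protocol). Three quantities are assumed, since the protocol gives none of them:
- *a*, the share of started operations that end without the device
- *r*, the complication rate among implanted subjects
- *c*, the share of abandoned cases with a complication

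Formulas:
- Abandoned cases: m = 500a/(1 − a)
- Rate over all started operations: (500r + mc)/(500 + m) = (1 − a)r + ac
- Difference from the reported rate: a(c − r)

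Abandoned cases: at a = 0.5%, m = 500 × 0.005/0.995 = 2.5; at 1%, 500 × 0.01/0.99 = 5.1; at 2%, 500 × 0.02/0.98 = 10.2.

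Rate over all started operations in the extreme case c = 1 (every abandoned case had a complication):

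| a | m | r = 2% | r = 5% | r = 10% |
|---|---|---|---|---|
| 0.5% | 2.5 | 2.49% | 5.47% | 10.45% |
| 1% | 5.1 | 2.98% | 5.95% | 10.90% |
| 2% | 10.2 | 3.96% | 6.90% | 11.80% |

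The difference a(1 − r) is always below a, so the rise is at most about 0.5 percentage points at a = 0.5% and about 2 at a = 2%.

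A milder case: with a = 1%, r = 2% and one in five abandoned cases having a complication (c = 20%), the difference is 0.01 × (0.20 − 0.02) = 0.18 points. In counts, (10 + 1)/(500 + 5) = 2.18% against 10/500 = 2.00%.

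The sign of the difference is that of c − r. The reported rate is too low when complications are commoner among abandoned cases than among implanted ones, as is to be expected where a complication caused the abandonment.

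**The case against.** **The cohort is deliberate.** The Synopsis and Study Design consistently define the group as implanted patients, and the safety endpoint is worded around the implant. This stands for survivorship and device safety. It does not settle procedural events, which Operative Procedure Information, the Adverse Events section and the Schedule of Events all bring into collection.

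**Events could still be reported.** A reader might infer that an abandoned case can have no adverse event report at all. The protocol does not support that. It calls people subjects before enrolment (Informed Consent, Screening), its adverse event definition extends to persons other than subjects, serious events go to the sponsor within 24 hours whatever their relationship to the study, and nothing forbids a form for a consented patient who was not implanted. This stands, and it limits the point to the absence of any rule that places such a case in the tabulated proportion or its denominator.

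**Nothing shows that abandoned cases are the most severe.** A reader might also infer that the worst intra-operative outcomes are removed. The protocol has no data on why operations are abandoned or how severe those cases are. Complications in completed implantations are captured, and a change to an INBONE II talar component stays within the study because those parts are in its product table.

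**Pre-operative forms.** It is tempting to see a separate contradiction in forms scheduled before surgery that carry a number assigned after it. The protocol does not say that the code must be present when data are first captured. Medical records are source documents, so forms can be coded after surgery. This is an administrative matter only.

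**Analysis sets belong in the analysis plan.** Largely true of population definitions. The timing of numbering and the forms to be completed are protocol matters, however, and an analysis plan cannot recover data that were never captured.

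**Conclusion.** The point holds as a limited but worthwhile improvement. As written, the enrolment and numbering rules give an operation that is started and ends without the device no assured place in the procedural complication proportions. Where a complication caused the abandonment, the reported rate is biased downwards.

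The size is unknown and probably small. The upper limit of about 0.5 to 2 percentage points rests on two assumptions: that 0.5% to 2% of started operations are abandoned, and that every one of those cases had a complication. With fewer complications among them the difference is smaller, and it vanishes if their complication rate equals that of implanted subjects. The safety endpoint is descriptive, with no comparator or threshold that a few cases would tip.

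The primary endpoint is not affected. A reader might infer that survivorship is also biased, but it concerns implanted devices and is rightly confined to implanted subjects.

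**What to change.** Amend the protocol as follows:

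- **Numbering:** assign the subject number at consent, once eligibility is confirmed. The target of 500 can still be counted in implanted subjects.
- **Data capture:** complete the operative and adverse event forms for every started operation, including those that end without the device, and record the reason.
- **Reporting:** give the number of such cases and their complications beside the rate in implanted subjects, and add a procedural complication rate over all started operations.
- **Survivorship:** keep it restricted to implanted subjects.

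The cost is a change of wording, a few extra forms, gaps in the numbering of the implanted series and, probably, a slightly less favourable complication rate.
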